11.10. Study Vaccination Pausing Rules

The investigator and the SRP will monitor the study vaccination pausing rules. If study vaccination is considered to raise significant safety concerns, further vaccination of subjects will be suspended until DRC review is carried out and subsequent communication between the sponsor and the investigators takes place.

The occurrence of any of the following events will lead to suspension of further study vaccination, and trigger a meeting of the DRC to discuss study suspension, adaptation or discontinuation of further vaccination:

1. One or more subject experience an SAE or other potentially life-threatening (Grade 4) event that is determined to be related to study vaccine; *OR*
2. One or more subjects experience anaphylaxis clearly not attributable to other causes than vaccination with study vaccine; *OR*
3. Two or more subjects experience a Grade 3 or 4 unsolicited AE of the same type, determined to be related to study vaccine, that persists for 72 hours or longer; *OR*
4. Two or more subjects experience a Grade 3 or 4 solicited systemic AE of the same type, determined to be related to study vaccine, that persists for 72 hours or longer; *OR*
5. Two or more subjects experience a persistent (upon repeat testing) Grade 3 or 4 laboratory abnormality related to the same laboratory parameter and considered related to study vaccine, that persists for 72 hours or longer; *OR*
6. Death of any subject, regardless of causality.

If any of the above specific pausing rules are met, the DRC will make recommendations regarding the continuation of the study to the sponsor. Study suspensions or terminations will occur within 5 working days after the decision is made, unless local regulations specify a shorter timeframe. Local regulatory authorities including IECs/IRBs will be informed within the appropriate regulatory-mandated timeframes. A study may be resumed only upon approval of a substantial amendment to the initial study application by the local regulatory authorities and IECs/IRBs. The sponsor will communicate conclusions regarding study continuation to the investigators, the IECs/IRBs and the national regulatory authorities as appropriate.

The investigator may ask for a review meeting to be held for any single event or combination of multiple events which, in his/her professional opinion, jeopardize the safety of the subjects or the reliability of the data.

Vaccinations for the study may be suspended for safety concerns other than those described above or before pausing rules are met if, in the judgment of investigator, subject safety may be threatened. The sponsor should be notified that the DRC will need to be convened.

This is a single site study so stopping rules will automatically apply to the entire study. Sponsor activities and responsibilities related to temporary study suspension and restart are described in the sponsor's applicable standard operating procedures (SOPs).^{17,18}

12. ADVERSE EVENT REPORTING

Timely, accurate, and complete reporting and analysis of safety information from clinical studies are crucial for the protection of subjects, investigators, and the sponsor, and are mandated by regulatory agencies worldwide. The sponsor has established SOPs in conformity with regulatory

requirements worldwide to ensure appropriate reporting of safety information; all clinical studies conducted by the sponsor or its affiliates will be conducted in accordance with those procedures.

Method of Detecting Adverse Events and Serious Adverse Events

Care will be taken not to introduce bias when detecting AEs or SAEs. Open-ended and non-leading verbal questioning of the subject is the preferred method to inquire about AE occurrence. For some studies, subjects are not always able to provide valid verbal responses to open-ended questions. In these circumstances, another method of detecting these events is specified.

Solicited Adverse Events

Solicited AEs are pre-defined local (ie, at the injection site) and systemic events for which subjects are specifically questioned and which are noted by subjects in their diaries (see Section 9.1.1).

Unsolicited Adverse Events

Unsolicited AEs are all AEs for which subjects are specifically not questioned in the subject diary.

12.1. Definitions

12.1.1. Adverse Event Definitions and Classifications

Adverse Event

An AE is any untoward medical occurrence in a clinical study subject administered a medicinal (investigational or non-investigational) product. An AE does not necessarily have a causal relationship with study vaccine. An AE can therefore be any unfavorable and unintended sign (including an abnormal finding), symptom, or disease temporally associated with the use of a medicinal (investigational or non-investigational) product, whether or not related to that medicinal (investigational or non-investigational) product (Definition per International Conference on Harmonisation [ICH]).

This includes any occurrence that is new in onset or aggravated in severity or frequency from the baseline condition, or abnormal results of diagnostic procedures, including laboratory test abnormalities.

Note: In this study, the sponsor will collect unsolicited AEs from ICF signature until 28 days after vaccination, and from the entry into the Unit until 28 days after challenge, and solicited AEs from the time of vaccination for 7 days post-vaccination (refer to Section 12.3.1). SAEs will be collected from ICF signature for the duration of the study.

Serious Adverse Event

An SAE based on ICH and European Union (EU) Guidelines on Pharmacovigilance for Medicinal Products for Human Use is any untoward medical occurrence that at any dose:

- Results in death
- Is life-threatening
(The subject was at risk of death at the time of the event. It does not refer to an event that hypothetically might have caused death if it were more severe.)
- Requires inpatient hospitalization or prolongation of existing hospitalization
- Results in persistent or significant disability/incapacity
- Is a congenital anomaly/birth defect
- Is a suspected transmission of any infectious agent via a medicinal product
- Is Medically Important*

*Medical and scientific judgment should be exercised in deciding whether expedited reporting is also appropriate in other situations, such as important medical events that may not be immediately life-threatening or result in death or hospitalization but may jeopardize the subject or may require intervention to prevent one of the other outcomes listed in the definition above. These should usually be considered serious.

If a serious and unexpected AE occurs for which there is evidence suggesting a causal relationship between the study vaccine and the event (eg, death from anaphylaxis), the event must be reported as a suspected unexpected serious adverse reaction (SUSAR) by the sponsor to health authorities and by the investigator to the IRB/IEC according to regulatory and local requirements.

Unlisted (Unexpected) Adverse Event/Reference Safety Information

An AE is considered unlisted if the nature or severity is not consistent with the applicable product reference safety information. For Ad26.RSV.preF, the expectedness of an AE will be determined by whether or not it is listed in the Investigator's Brochure.¹

Adverse Event Associated With the Use of the Vaccine

An AE is considered associated with the use of the vaccine if the attribution is related by the definitions listed in Section [12.1.2](#).

12.1.2. Attribution Definitions

Every effort should be made by the investigator to explain any AE and assess its potential causal relationship, ie, to administration of the study vaccine, to viral challenge or to alternative causes (eg, natural history of the underlying diseases, concomitant therapy). This applies to all AEs, whether serious or non-serious.

Note: AEs occurring from ICF signature until 28 days after vaccination will be examined for relationship to study vaccine. AEs occurring from admission to the quarantine Unit until 28 days after challenge will be evaluated for relationship to the challenge.

Causality of AEs should be assessed by the investigator based on the following:

Related: there is suspicion that there is a relationship between the study vaccine (or viral challenge) and the AE (without determining the extent of probability); there is a reasonable possibility that the study vaccine (or viral challenge) contributed to the AE.

Unrelated: there is no suspicion that there is a relationship between the study vaccine (or viral challenge) and the AE; there are other more likely causes and administration of the study vaccine (or viral challenge) is not suspected to have contributed to the AE.

By definition, all solicited AEs at the injection site (local) will be considered related to the study vaccine administration.

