1.1. Background

RSV is considered to be the most important cause of serious acute respiratory illness in infants and children under 5 years of age.^{16,34,38} Globally, in 2005, RSV was responsible for an estimated 3.4 million hospitalizations worldwide in children under 5 years of age. Furthermore, 66,000 to 199,000 children younger than 5 years died from RSV-associated acute lower respiratory tract infection (LRTI) in 2005, and 99% of these deaths occurred in developing countries.²⁷ Nevertheless, the disease burden due to RSV in developed countries is substantial, with RSV infection during childhood linked to the development of wheezing, airway hyperreactivity and asthma.^{31,33,35,36,37} In the United States (US), the infection rate was 68.8% in children younger than 12 months of age and 82.6% during the second year of life. Virtually all children had been infected at least once by 24 months of age, and about one half had experienced 2 infections.¹⁴ In the US, RSV infection in children under 5 years of age is the cause of 57,000 to 175,000 hospitalizations, 500,000 emergency room visits, and approximately 500 deaths each year.^{30,34,38} In children under 1 year of age, RSV is the most important cause of bronchiolitis, and RSV hospitalization is highest among children under 6 months of age.^{6,16}

In addition to children, RSV is an important cause of respiratory infections in the elderly, immunocompromised, and those with underlying chronic cardiopulmonary conditions.¹⁰ In long-term care facilities, RSV is estimated to infect 5-10% of the residents per year with significant rates of pneumonia (10 to 20%) and death (2 to 5%).¹¹ In one epidemiology study of RSV burden, it was estimated that 11,000 elderly persons die annually of RSV in the US.³⁹ These data support the importance of developing an effective vaccine for certain adult populations.

Despite the high disease burden, no licensed vaccine is available for RSV. The first vaccine candidate for young children, which consisted of formalin-inactivated RSV (FI-RSV), was associated with enhanced respiratory disease (ERD) upon infection with RSV.¹⁹ Although the mechanisms for ERD are not fully understood, it is thought that FI-RSV failed to induce adequate neutralizing antibody titers and CD8 priming, and induced a T-helper (Th) 2 skewed response.²⁶

Adenoviral-vectored Vaccines

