9.2.6. Safety Evaluations

Any clinically relevant changes occurring from ICF signature until discharge from the Unit must be recorded on the eCRF. Any clinically significant abnormalities, including those persisting at the end of the study/early withdrawal, will be followed by the investigator until resolution or until a clinically stable endpoint is reached.

Adverse events occurring from ICF signature until 28 days after vaccination will be examined for relationship to study vaccine. Adverse events occurring from admission to the quarantine Unit until 28 days after challenge will be evaluated for relationship to the challenge.

The study will include the evaluations of safety and tolerability outlined in the following sections according to the timepoints provided in the [Time and Events Schedule](#).

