11.7. Safety Analyses

No formal statistical testing of safety data is planned. All safety data will be analyzed descriptively by regimen.

Adverse Events

The verbatim terms used in the eCRF by investigators to identify AEs will be coded using the Medical Dictionary for Regulatory Activities (MedDRA). All reported AEs with onset during the

active phases (ie, AEs emerging after vaccination up to 28 days post-vaccination or during the quarantine phase), and all SAEs, will be included in the analysis. For each AE, the percentage of subjects who experience at least one occurrence of the given event will be summarized by group separately for the vaccination phase and challenge phase.

Summaries, listings, datasets, or subject narratives may be provided, as appropriate, for those subjects who die, who discontinue study vaccine due to an AE, or who experience a severe AE or an SAE.

Summaries and/or listings may be provided separately for AEs with onset outside the active phases.

Solicited local (at injection site) and systemic AEs will be summarized descriptively. The overall frequencies per vaccine group as well as frequencies according to severity and duration will be calculated for solicited AEs. In addition, the number and percentages of subjects with at least one solicited local (at injection site) or systemic AE will be presented. Frequencies of unsolicited AEs, separately for all and vaccination-related only, will be presented by System Organ Class and preferred term. Unsolicited AEs will be presented separately for vaccination phase and quarantine phase.

Clinical Laboratory Tests

Laboratory abnormalities will be determined according to the FDA Guidance document (see [Attachment 1](#)), or in accordance with the normal ranges for the clinical laboratory parameter if no grades are available. If a laboratory value falls within the grading as specified in the FDA table, but also within the laboratory normal limits, the value is considered as normal. Emerging abnormalities will be tabulated.

Vital Signs

A tabulation of the distribution of temperatures per half-degree intervals will be provided. For systolic and diastolic blood pressures, heart rate and respiratory rate, the percentage of subjects with values beyond clinically relevant limits will be summarized.

Electrocardiogram

Any abnormalities in ECG parameters (at screening and on admission to the Unit) will be listed.

Physical Examination

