12.3. Procedures

12.3.1. All Adverse Events

Unsolicited AEs and special reporting situations will be reported from ICF signature until 28 days after vaccination, and from the entry into the Unit until 28 days after challenge.

From challenge until discharge from the Unit, SSC findings greater than Grade 0 will be presumed to represent virus infection consequent to challenge, and will not additionally be captured as an AE, unless they meet the criteria for an SAE. The changes in RSV viral load will not be reported as AEs or SAEs.

Solicited AEs will be recorded by each subject in the subject diary for 7 days after dosing. The investigator will review each subject's diary at the subsequent in-clinic visit; diary information will be transcribed by the study personnel in the on-site assessment forms in the eCRF.

The sponsor will evaluate any safety information that is spontaneously reported by an investigator beyond the time frame specified in the protocol.

The investigator will monitor and check the study data including all AE and any clinical laboratory data as they become available and will make determinations regarding the severity of the adverse experiences and their relation to study vaccine. All AEs will be deemed related to study vaccine or not related to study vaccine, or related to the viral challenge or not related to viral challenge, according to Section 12.1.2.

The investigator must review both post-injection reactogenicity and other AEs to insure the prompt and complete identification of all events that require expedited reporting as SAEs, invoke pausing rules or are other serious and unexpected events.

All AEs, regardless of seriousness, severity, or presumed relationship to study vaccine, must be recorded using medical terminology in the source document and the eCRF. Whenever possible, diagnoses should be given when signs and symptoms are due to a common etiology (eg, cough,

runny nose, sneezing, sore throat, and head congestion should be reported as “upper respiratory infection”). The investigator must record in the eCRF their opinion concerning the relationship of the AE to study vaccine. All measures required for AE management must be recorded in the source document and reported according to sponsor instructions.

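### The causality windows in 9.2.6 and the 12.1.2 Note state no vaccine assessment after a challenge at day 28 or later, and conflict with the all-AE rule in 12.1.2 and the eCRF requirement in 12.3.1

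*Protocol*

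**What the plan says.** Protocol 9.2.6 gives the first window: "Adverse events occurring from ICF signature until 28 days after vaccination will be examined for relationship to study vaccine". The Note in 12.1.2 repeats it and adds the second: "AEs occurring from admission to the quarantine Unit until 28 days after challenge will be evaluated for relationship to the challenge". Section 9.2.6 carries both windows but not the general rule.

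The general rule is the first paragraph of 12.1.2, directly above the definitions. The investigator is to explain any AE and "assess its potential causal relationship, ie, to administration of the study vaccine, to viral challenge or to alternative causes". The paragraph says that this covers all AEs, serious or not. An event counts as related if there is a reasonable possibility that the vaccine or the challenge contributed to it; sole causation is not required.

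Section 12.3.1 says "All AEs will be deemed related to study vaccine or not related to study vaccine, or related to the viral challenge" or not related to it, and refers back to 12.1.2. Later in the same section the investigator must enter in the eCRF an opinion on each AE's relationship to study vaccine. No time limit is given there.

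Three things downstream use vaccine attribution:
- **Tables.** Protocol 11.7: "Frequencies of unsolicited AEs, separately for all and vaccination-related only, will be presented by System Organ Class and preferred term", with the vaccination and quarantine phases shown separately. SAP 7.1.2 lists a table of related unsolicited AEs, SAP 7 presents safety by period, and SAP Table 2 defines a Post-Challenge period.
- **Pausing.** Rule 1 in 11.10: "One or more subject experience an SAE or other potentially life-threatening (Grade 4) event that is determined to be related to study vaccine". Rules 3, 4 and 5 also need a judgement that the event is related to study vaccine, and rule 2 needs anaphylaxis attributed to it. No rule carries a time limit.
- **Expedited reporting.** Section 12.1.1 defines vaccine-associated AEs by the attribution in 12.1.2, and SUSAR reporting rests on evidence of a causal link with the vaccine.

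**The concern.** This is a vaccine-plus-challenge design. Section 1.1 of the protocol recalls that the first RSV vaccine candidate for young children "was associated with enhanced respiratory disease (ERD) upon infection with RSV". An event of that kind needs the vaccine first and the virus later. In this trial it would be expected mainly after inoculation, which is the period that the windows give to the challenge. The definition of related allows an event to be attributed to both exposures, but the Note does not ask for both.

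If a blinded investigator takes the Note as the operating instruction, a serious respiratory event after challenge may be scored against the virus and given no vaccine attribution. It would then be absent from the vaccination-related tables and would not meet a pausing rule that depends on that attribution. Timing matters here. Section 3.1 uses the withdrawal rate between vaccination and challenge in the first cohort to decide how many subjects to vaccinate for later cohorts, so some vaccination is expected to follow the first challenges.

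**Working it through.** The plan states no figure on this point, so there is none to reproduce. The check is date arithmetic on the windows, then a comparison of the passages.

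**Inputs.** Vaccine window: to day 28 after vaccination (9.2.6, 12.1.2 Note). Challenge window: from Unit admission to 28 days after challenge (same places). Vaccination-to-challenge interval C: target 28 days, allowed 24 to 90 (9.1.5.2). Admission: one or two days before challenge (9.1.5.1). Final contact: Day 155 in the Time and Events Schedule, where vaccination is Day -28, so 155 + 28 = 183 days after vaccination.

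**Formulas**, reading the Note on its own:
- Days after challenge still inside the vaccine window = max(0, 28 − C), out of 28.
- Elapsed overlap of the two windows = 28 − (C − 1) or 28 − (C − 2), that is 29 − C or 30 − C, floored at 0.
- Days of SAE follow-up after the challenge window closes = 183 − (C + 28).

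| C (days) | Post-challenge days in vaccine window | Overlap counted from admission (days) | SAE days after both windows |
|---|---|---|---|
| 24 | 4 of 28 (14%) | 5 to 6 | 183 − 52 = 131 |
| 28 | 0 of 28 | 1 to 2 | 183 − 56 = 127 |
| 60 | 0 of 28 | 0 | 183 − 88 = 95 |
| 90 | 0 of 28 | 0 | 183 − 118 = 65 |

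The Note alone therefore leaves 24 to 28 of the 28 post-challenge days without a stated vaccine assessment.

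**The passages side by side:**
- The 12.1.2 Note and 9.2.6 are specific and windowed: vaccine first, challenge afterwards.
- The first paragraph of 12.1.2 is general and has no window: vaccine, challenge and other causes, for all AEs.
- The eCRF sentence in 12.3.1 requires the vaccine relationship for every AE, without a window.
- The classification sentence in 12.3.1 joins vaccine and challenge with *or* and points back to 12.1.2, so it returns the reader to the conflict.

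Two competent readers could follow this text and record different data for the same post-challenge event.

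**Which pausing rules are exposed.** Rule 6 (any death) needs no attribution. Rule 4 concerns solicited systemic AEs, collected for 7 days after vaccination, so it is closed before the earliest challenge at day 24. Rule 2 concerns anaphylaxis from vaccination and is not in practice a post-challenge matter. That leaves mainly rules 1, 3 and 5.

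**The case against.** A reader might infer more: that vaccine causality is shut off at challenge, that later events are judged against the virus alone, and that vaccine-enhanced disease can be neither counted as vaccine-related nor trigger a pause. The documents do not support that. The Note contains no exclusive word. The first paragraph of 12.1.2 covers all AEs, contribution is enough for an event to be related, and 12.3.1 requires the vaccine opinion to be entered. An investigator relying on those sentences can call a post-challenge SAE vaccine-related, and rule 1 is then met. Nor is the post-challenge count of vaccine-related AEs zero by construction. It would be so only if the required eCRF entry were left blank or answered negatively whenever the Note's vaccine window had closed.

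There are also routes that need no vaccine attribution. These are pausing rule 6, an investigator-requested review of any event, and suspension for other safety concerns (all 11.10); DRC review of significant or unexpected safety issues, unblinded if necessary (11.9); and the provision in 17.9.2 for termination, after discussion, because of severe or clinically significant illness from challenge. AEs are tabulated by group and phase whatever their attribution, and symptom scores, mucus weight, viral load and spirometry are summarised as efficacy data. With a blinded investigator, an excess in the vaccine arm may show more clearly there than in causality judgements.

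The background should not be stretched either. Section 1.1 describes enhanced disease with one formalin-inactivated candidate and reports no histopathological signs of it in cotton rats given this vaccine. The plan also anticipates natural RSV infection (11.1), so challenge is not the only possible occasion for such an event.

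All of this stands, and it limits the harm. It does not remove the conflict, correct the related-AE tables, or replace a recorded vaccine attribution.

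**Conclusion.** The point holds as an internal inconsistency that should be corrected. The stated windows give no vaccine assessment for any of the 28 days after challenge when challenge is at day 28 or later, and for 24 of 28 days at the earliest permitted challenge. SAEs more than 28 days after challenge are in neither window: 127 days of follow-up at the target schedule. These counts describe the Note read literally. They do not estimate how often an attribution would be missed, which depends on which sentence the site follows.

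The consequence rests on two assumptions: that a site treats the Note as the operative instruction, and that the event is one to which vaccine and virus both contributed. In that case the vaccination-related tables, SUSAR classification and pausing rules 1, 3 and 5 could miss it, with the backstops above giving partial cover.

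One limit lies outside this point. From challenge to discharge, symptom-card findings above Grade 0 are presumed due to the virus and are not recorded as AEs unless serious (9.2.4, 12.3.1). Non-serious enhanced symptoms in that period would therefore not enter the AE data under either reading.

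**What to change.** Reconcile 9.2.6, the 12.1.2 Note and the classification sentence in 12.3.1 with the first paragraph of 12.1.2. State that every recorded AE from Unit admission, and every SAE to the end of the study, is assessed for relationship to study vaccine and, separately, to viral challenge, in two eCRF fields. State in 11.7 and SAP 7.1.2 that vaccination-related frequencies are taken from the vaccine field in both phases. The sponsor should also reconcile 11.10 with the revised attribution wording; no pausing threshold is proposed or changed here.

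The cost is protocol and SAP wording, one further eCRF causality field, and one extra investigator judgement per post-challenge AE. The change does not reach non-serious symptom-card findings up to discharge; for those the by-arm symptom summaries remain the source.
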